This study involves no delay to treatment, no medication taper, all participants receive active treatment. Participants are asked to not change their medication while admitted to the research unit. They can change medications during the follow-up phase. The Columbia Suicide Severity Rating Scale (CSSRS) will be used at screening, administered by a study physician. Any participant reporting suicidal ideation or behavior (defined as any answer of 'yes' to questions 1, 2 or 6 on CSSRS) to any member of the research team will be evaluated by Drs. [name], [name], or [name]. If the patient is an active suicide risk, 911 will be called and/or the participant will be escorted to the Emergency Department. If the participant is not an active risk, they will be provided with referrals for outpatient treatment. If the participant has outpatient treatment in place, their clinician will be notified. [name], [name], or [name] will follow up with the participant until their clinical care is in place.

The C-SSRS is done at screening. After this, the Beck Depression Inventory (BDI) is acquired during the inpatient stay and during the follow up period. The BDI is a self-report measure. The BDI will be used to assess risk and any of the following criteria will trigger a clinical assessment by a psychiatrist regarding suicide risk: 1) an answer of "yes" to question 9 (thoughts of killing self); 2) a score higher than 16; 3) an increase in BDI score of 10 points or more from the baseline BDI (obtained on scan day) even if the total score remains below 16. Please note that the follow up assessments include a phone call with a study psychiatrist. As mentioned above, the psychiatrists are Drs. [name], [name], or [name]. Participants will be advised that they can call the lab to speak with a psychiatrist when the link is sent. A research assistant will check the responses on the day that they are sent to check the responses.

Recruitment Procedures

This section will include all information regarding your study's recruitment process/procedures.

Describe settings where recruitment will occur. Participants will be recruited using advertisements from Facebook and Craig's list (not limited to NYC)

How and by whom will subjects be approached and/or recruited? N/A

How will the study be advertised/publicized? Facebook and Craigslist

Attach any ads/recruitment materials requiring review at this time in the Uploads section.

Clinical Trials:

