- k) The Defense and Veterans Pain Rating Scale (DVPRS), a graphic tool that clinicians use to facilitate self-reported pain from patients, including the supplemental questions. The DVPRS is similar to the BPI but is more widely used in Veteran populations.
- l) MRI safety screening form: standard form used to assess for metal and other risks associated with MRI.

Following screening, participants who are eligible will be consented for the full study. This will include a review of the procedures and risks of the study. Participants will be informed that all procedures are voluntary and that questions can be asked at any point. The consent form can be signed either through REDCap with an e-signature or in person.

Participants will be asked if they want to provide information for an emergency contact, which is not mandatory, on admission to the inpatient unit.

Protocol Summary Form

The additional assessments obtained on the scan (baseline) day include:

- a) Columbia Autobiographical Memory Interview – short form (AMI-SF), which is used to assess memory changes in studies of ECT.
- b) Trail Making Test (TMT), Parts A and B, to assess executive function.
- c) The Stroop Color Word Test to also assess executive function.
- d) Repeatable Battery for the Assessment of Neuropsychological Status, which is a brief, individually administered battery to measure cognitive decline or improvement across five domains: immediate memory, visuospatial skills, language, attention, and delayed memory.
- e) Montreal Cognitive Assessment (MoCA), a quick (5-10 min) measure of cognition which uses a 10-item, 30-point (30=best score) scale.
- f) The Timeline Followback (TLFB): to obtain quantitative estimates of alcohol, tobacco, cannabis, and other drug use (including prescribed medications, like opioids and benzodiazepines). We will ask about substance use for time between screening and baseline.

TEST sessions: Following the MRI and safety read of the scan, subjects will be scheduled for the TEST sessions.

Participants will be asked to have no food or drink after 9 pm the night before (NPO). The following assessments will be obtained during the inpatient admission after TEST sessions start.

- a) The Brief Pain Inventory (BPI): a self-administered questionnaire (0- 10, developed to quantify measures of pain (weekly)

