- b) Clinical Global Impression (CGI) scale, a measure of symptom severity, treatment response and the efficacy of treatments as measured by a study physician (three days week).
- c) Beck Depression Inventory (BDI): the 21 item self-report rating scale for depression (weekly).
- d) Beck Anxiety Inventory (BAI): the 21 item self-report rating scale for anxiety (weekly).
- e) The Defense and Veterans Pain Rating Scale (DVPRS), a graphic tool that clinicians use to facilitate self-reported pain from patients, including the supplemental questions (weekly).

Subjects will be asked to confirm that they have had no food or drink for 8 hours with the exception of required prescription medication which they can take by mouth on the morning of the procedure with a small sip of water. They will then be asked to change into a hospital gown, escorted to the ECT suite. Vital signs (blood pressure, heart rate, and oxygen saturation) will be recorded at baseline and every 5 minutes through the end of the procedure. EEG leads will be placed in the middle of the forehead and on the left mastoid to monitor for any seizure activity. The EEG output will be reviewed to assess the absence of a seizure.

General anesthesia will be performed by an anesthesiologist. TEST will be sub-convulsive, but since seizure threshold determination for ECT involves sub-convulsive stimulation and is done routinely, there are no substantial differences or additional risks with TEST.

Protocol Summary Form

The absence of a seizure will be verified per usual ECT protocol by observing for tonic-clonic movements in a lower extremity isolated from neuromuscular blockade by a blood pressure cuff maintained above systolic blood pressure and with interpretation of the electroencephalogram (EEG) generated from the electrodes placed in the center of the forehead and one each on the left and right mastoid processes.

In the event that a subject has a seizure, the TEST dose will be lowered to 1/10th of the ECT dose (from 1/8th). The seizure will be discussed with the participant, including the plan to reduce the dose. If a participant has a seizure at 1/10th dose, they will be discontinued from the study.

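### The BDI-rise suicide-risk trigger refers to a scan-day BDI that the scan-day list omits, and pain and HDRS are listed before TEST only at screening; add both before session 1

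*Combined protocol and SAP*

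**What the plan says.** **Suicide Risk Management Plan.** The C-SSRS is given at screening. On timing from then on, the plan says: "After this, the Beck Depression Inventory (BDI) is acquired during the inpatient stay and during the follow up period". Three BDI findings lead to a psychiatric assessment: endorsement of item 9, a total above 16, or "an increase in BDI score of 10 points or more from the baseline BDI (obtained on scan day". The section adds a safeguard: "Please note that the follow up assessments include a phone call with a study psychiatrist".

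**Study procedures narrative.**
- Screening list: includes HDRS, BDI, BPI, McGill, PROMIS-29, DVPRS and TLFB.
- Scan day: introduced by "The additional assessments obtained on the scan (baseline) day include", followed by AMI-SF, Trail Making, Stroop, the repeatable neuropsychological battery, MoCA and TLFB. The TLFB entry has its own recall period: "We will ask about substance use for time between screening and baseline". There is no BDI, HDRS or pain scale.
- Next step: "Following the MRI and safety read of the scan, subjects will be scheduled for the TEST sessions".
- Inpatient list: "The following assessments will be obtained during the inpatient admission after TEST sessions start". It holds weekly BPI, DVPRS and BAI, a physician-rated CGI three days a week, and "Beck Depression Inventory (BDI): the 21 item self-report rating scale for depression (weekly".
- Before discharge: HDRS, BDI and the pain scales are repeated. Weekly telephone follow-up for a month includes BPI and BDI.

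**Specific Aims and Hypotheses.** Aim 1 sets preliminary efficacy in advance as a pain decrease of at least 30%. Aim 2 looks for an improvement of at least 30% in depressive symptoms as well as pain. The Background section places ratings of pain, mood and memory before and after TEST but gives no day for the first of these.

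**The concern.** There are two separate problems with the same cheap remedy.

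**The safety rule.** It is defined as a change from a value that the schedule does not list. If staff work from the visit lists, the scan-day BDI may not be taken and the screening score may be used in its place. A screening score above the true pre-treatment score can then hide a 10-point rise. The C-SSRS is listed only at screening, so from then on the BDI is the instrument the risk plan relies on.

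**The pain baseline.** Pain carries the 30% criterion, yet its only listed value before TEST is at screening. Consent, the MRI, the safety read and scheduling all come between that value and session 1, and no interval is stated. The request to keep medication unchanged covers the inpatient stay, not this earlier period. There is no control group, so change before the first session cannot be told apart from change during treatment. The HDRS has the same gap for Aim 2. The cognitive battery does get a scan-day value.

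**Working it through.** The plan gives no figure to reproduce here. The check sets the schedule out side by side and then works out where each gap can matter.

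**1. Listed assessments by time point (study procedures narrative)**

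| Measure | Screening | Scan day | After TEST starts | Before discharge |
|---|---|---|---|---|
| BDI | yes | no | weekly | yes |
| BPI, DVPRS | yes | no | weekly | yes |
| McGill | yes | no | no | yes |
| HDRS | yes | no | no | yes |
| TLFB | yes | yes | no | no |

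The risk plan's account of BDI timing after screening also names only the inpatient stay and follow-up.

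**2. Where the BDI-rise trigger acts alone**

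Inputs: rise of 10 or more; total above 16; item 9 (all from the Suicide Risk Management Plan). Let b be the baseline and c the current total, with item 9 not endorsed. The rise rule adds something only if c - b ≥ 10 and c ≤ 16.
- Then b ≤ 16 - 10 = 6, and c ≥ 0 + 10 = 10.
- So the rule acts alone only for b from 0 to 6 and c from 10 to 16.
- For b = 7, a 10-point rise gives 17, and the cutoff already fires.

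Example of a missed rise: screening 3, scan day 0, inpatient 11.
- From scan day: 11 - 0 = 11, which triggers.
- From screening: 11 - 3 = 8, which does not. The total of 11 is not above 16, so the cutoff does not fire either.

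The error can go the other way. A screening score below the scan-day score makes the rule fire more readily.

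**3. How pre-treatment change enters the 30% criterion**

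Assume that the criterion is applied per participant and that screening is the baseline; the documents state neither. Let S be the screening score and d the fall before session 1 (negative for a rise). The target is 0.7 × S, so the fall still needed from the session 1 level is

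((S - d) - 0.7 × S) / (S - d).

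For S = 6 and d = 1: (5 - 4.2) / 5 = 16.0%. For S = 6 and d = -1: (7 - 4.2) / 7 = 40.0%.

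| S | d = 0.5 | d = 1 | d = -1 |
|---|---|---|---|
| 4 | 20.0% | 6.7% | 44.0% |
| 5 | 22.2% | 12.5% | 41.7% |
| 6 | 23.6% | 16.0% | 40.0% |
| 7 | 24.6% | 18.3% | 38.8% |
| 8 | 25.3% | 20.0% | 37.8% |

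The values of S and d are illustrations. Nothing in the documents gives the drift, its direction or the interval.

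**The case against.** **The BDI gap may be only an omission from a list.** The risk plan is operative text and says the BDI is taken on scan day. The scan-day list is headed as additional assessments and says that it includes the items named, so it need not be exhaustive. TLFB may be relisted only because its recall period changes. This has some force: the BDI may well be taken in practice. It is still the weaker reading, because a screening instrument that is repeated that day is written out, and the risk plan's own timing statement leaves scan day out. Either way, one added line settles it.

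**The safety consequence is limited.** This stands. Harm requires that the scan-day BDI is not taken, that screening is substituted, and that the screening score is higher by enough to bring the rise below 10, all within the narrow range shown. Item 9, the cutoff of 16, physician contact on the unit and psychiatrist calls in follow-up all remain. A reader might infer that participants are left unmonitored for suicide risk. The documents do not support that.

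**The pain part is a preference.** A screening score does meet the promise of a rating before TEST, so there is no contradiction. No section names screening as the percent-change baseline, and the procedures attach the word baseline to scan day. The point is therefore conditional: it applies if the only listed value is the one used. A later baseline also leaves placebo response and natural change during treatment in the estimate. This too stands. It removes only the part of the change that falls before session 1.

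**Conclusion.** The point holds as two modest schedule defects that are worth fixing because the remedy is cheap.

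The rise trigger and the scan-day list do not agree. With item 9 not endorsed, this matters only for a baseline of 0-6 with a current score of 10-16. That shows where the rule works alone and is not a risk estimate.

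For pain, and for the HDRS under Aim 2, change before session 1 is mixed into the 30% criterion if screening is the baseline. The size and direction are unknown.

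Three stronger readings are tempting and not supported:
- *The pain result is biased in TEST's favour.* A rise before session 1 works against it, as the last column of the second table shows. Regression to the mean adds nothing unless participants are selected on pain score, and the documents reviewed show no entry threshold for pain.
- *The scan-day BDI is not being collected.* The documents show only that it is not listed.
- *The three participants who completed before the MRI-sharing collaboration (Methods to Protect Confidentiality) lack a later value.* That section does not say which scan-day measures they had. Some participants who have already completed may lack one; the number cannot be stated.

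**What to change.** 1. In the study procedures, add BDI, BPI and DVPRS, plus HDRS for Aim 2 participants, to the scan-day list or to the unit before session 1.
2. In the Suicide Risk Management Plan, name the last BDI before session 1 as the reference for the 10-point rise. This works whichever of the two days is chosen.
3. In Analysis and Outcomes, define the percent-change baseline for pain (and for HDRS under Aim 2) as the last value before session 1 where one exists, otherwise the screening value. Report change from screening for all participants as a sensitivity analysis, and state how many have each kind of baseline.

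The cost is a few minutes of questionnaires already in use, a short amendment, and mixed baselines that must be disclosed. No extra participants or visits are needed.

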Provide a clear, concise narrative of study procedures with special attention to the subjects' involvement. Detail the overall study timeline and location of study procedures, list all interventions, assessments and interviews, estimate the duration of each procedure, provide dosing schedules, identify study personnel involved in each procedure, and provide

Protocol Summary Form

credentials for relevant personnel. If treatment is provided, specify the minimum credentials for providing that treatment. For complicated study designs, we strongly encourage attaching tables, flow-charts, and study algorithms.

Potential subjects are required to have a diagnosis of CNCP, defined as pain that persists or recurs for more than 3 months or past the time of normal tissue healing). A medical and psychiatric interview (by a study physician), ECG, urine toxicology, and labs (comprehensive metabolic panel, complete blood cell count, urinalysis) will be performed during screening.

The following assessments will be obtained during screening:

- a) The Hamilton Depression Rating Scale (HDRS): the 24 item assessment scale regarding symptoms of depression.
- b) Beck Depression Inventory (BDI): the 21 item self-report rating scale for depression
- c) Beck Anxiety Inventory (BAI): the 21 item self-report rating scale for anxiety
- d) The Young Mania Rating Scale: a widely used 11 item rating scales used to assess manic symptoms.
- e) The Columbia Suicide Severity Rating Scale (CSSRS): a suicide risk assessment that uses a series of simple, plain-language questions to assess thoughts of suicide.
- f) The Brief Pain Inventory (BPI): a self-administered questionnaire (0- 10, developed to quantify measures of pain.
- g) McGill Pain Questionnaire a self-reported measure of pain studied with a number of diagnoses, and it assesses both the quality and intensity of pain.
- h) The Patient-Reported Outcomes Measurement Information System (PROMIS)-29, which assesses pain interference and quality of life.
- i) Mini-Mental Status Exam (MMSE), a 30 point a widely used test of cognitive function that includes tests of orientation, attention, memory, and language. The minimum score allowable for study entry is 24.
- j) The Timeline Followback (TLFB): a clinical research tool used to obtain quantitative estimates of alcohol, tobacco, cannabis, and other drug use (including prescribed medications, like opioids and benzodiazepines). We will ask about substance use for the month prior.
- k) The Defense and Veterans Pain Rating Scale (DVPRS), a graphic tool that clinicians use to facilitate self-reported pain from patients, including the supplemental questions. The DVPRS is similar to the BPI but is more widely used in Veteran populations.
- l) MRI safety screening form: standard form used to assess for metal and other risks associated with MRI.

Following screening, participants who are eligible will be consented for the full study. This will include a review of the procedures and risks of the study. Participants will be informed that all procedures are voluntary and that questions can be asked at any point. The consent form can be signed either through REDCap with an e-signature or in person.

Participants will be asked if they want to provide information for an emergency contact, which is not mandatory, on admission to the inpatient unit.

Protocol Summary Form

The additional assessments obtained on the scan (baseline) day include:

- a) Columbia Autobiographical Memory Interview – short form (AMI-SF), which is used to assess memory changes in studies of ECT.
- b) Trail Making Test (TMT), Parts A and B, to assess executive function.
- c) The Stroop Color Word Test to also assess executive function.
- d) Repeatable Battery for the Assessment of Neuropsychological Status, which is a brief, individually administered battery to measure cognitive decline or improvement across five domains: immediate memory, visuospatial skills, language, attention, and delayed memory.
- e) Montreal Cognitive Assessment (MoCA), a quick (5-10 min) measure of cognition which uses a 10-item, 30-point (30=best score) scale.
- f) The Timeline Followback (TLFB): to obtain quantitative estimates of alcohol, tobacco, cannabis, and other drug use (including prescribed medications, like opioids and benzodiazepines). We will ask about substance use for time between screening and baseline.

TEST sessions: Following the MRI and safety read of the scan, subjects will be scheduled for the TEST sessions.

Participants will be asked to have no food or drink after 9 pm the night before (NPO). The following assessments will be obtained during the inpatient admission after TEST sessions start.

- a) The Brief Pain Inventory (BPI): a self-administered questionnaire (0- 10, developed to quantify measures of pain (weekly)
- b) Clinical Global Impression (CGI) scale, a measure of symptom severity, treatment response and the efficacy of treatments as measured by a study physician (three days week).
- c) Beck Depression Inventory (BDI): the 21 item self-report rating scale for depression (weekly).
- d) Beck Anxiety Inventory (BAI): the 21 item self-report rating scale for anxiety (weekly).
- e) The Defense and Veterans Pain Rating Scale (DVPRS), a graphic tool that clinicians use to facilitate self-reported pain from patients, including the supplemental questions (weekly).

Subjects will be asked to confirm that they have had no food or drink for 8 hours with the exception of required prescription medication which they can take by mouth on the morning of the procedure with a small sip of water. They will then be asked to change into a hospital gown, escorted to the ECT suite. Vital signs (blood pressure, heart rate, and oxygen saturation) will be recorded at baseline and every 5 minutes through the end of the procedure. EEG leads will be placed in the middle of the forehead and on the left mastoid to monitor for any seizure activity. The EEG output will be reviewed to assess the absence of a seizure.

General anesthesia will be performed by an anesthesiologist. TEST will be sub-convulsive, but since seizure threshold determination for ECT involves sub-convulsive stimulation and is done routinely, there are no substantial differences or additional risks with TEST.

Protocol Summary Form

The absence of a seizure will be verified per usual ECT protocol by observing for tonic-clonic movements in a lower extremity isolated from neuromuscular blockade by a blood pressure cuff maintained above systolic blood pressure and with interpretation of the electroencephalogram (EEG) generated from the electrodes placed in the center of the forehead and one each on the left and right mastoid processes.

In the event that a subject has a seizure, the TEST dose will be lowered to 1/10th of the ECT dose (from 1/8th). The seizure will be discussed with the participant, including the plan to reduce the dose. If a participant has a seizure at 1/10th dose, they will be discontinued from the study.

Subjects will be monitored until they recover. The subjects' oxygen saturation, BP and heart rate must be back at baseline before discharge (oxygen saturation >95%, BP and HR within normal limits and within +/- 10 mmHg or BPM). The expected recovery time is 60 to 80 minutes. Subjects will remain in the recovery area until they are assessed by the physicians and ready to leave the ECT suite. Subjects will return to the inpatient unit after each TEST session when they are awake from anesthesia and have stable vital signs.

At the end of the TEST sessions, subjects will be asked to complete the following assessments prior to discharge from the unit:

- a) The Hamilton Depression Rating Scale (HDRS): the 24 item assessment scale regarding symptoms of depression.
- b) The Brief Pain Inventory (BPI): a self-administered questionnaire (0- 10, developed to quantify measures of pain
- c) The Defense and Veterans Pain Rating Scale (DVPRS), a graphic tool that clinicians use to facilitate self-reported pain from patients, including the supplemental questions.
- d) Columbia Autobiographical Memory Interview – short form (AMI-SF), which is used to assess memory changes in studies of ECT.
- e) Trail Making Test (TMT), Parts A and B, to assess executive function.
- f) The Stroop Color Word Test to also assess executive function.
- g) Repeatable Battery for the Assessment of Neuropsychological Status, which is a brief, individually administered battery to measure cognitive decline or improvement across five domains: immediate memory, visuospatial skills, language, attention, and delayed memory.
- h) Beck Depression Inventory (BDI): the 21 item self-report rating scale for depression
- i) Beck Anxiety Inventory (BAI): the 21 item self-report rating scale for anxiety
- j) The Patient-Reported Outcomes Measurement Information System (PROMIS)-29, which assesses pain interference and quality of life.
- k) McGill Pain Questionnaire a self-reported measure of pain studied with a number of diagnoses, and it assesses both the quality and intensity of pain.
- l) Clinical Global Impression (CGI) scale, a measure of symptom severity, treatment response and the efficacy of treatments as measured by a study physician.
- m) Montreal Cognitive Assessment (MoCA) test: a brief, simple screening for cognitive impairment.

Protocol Summary Form

Prior to discharge, participants who are not engaged in treatment for their chronic pain will be assisted with finding medical care for this condition. They will also be referred to psychiatric care if depression emerges or persists during the study. Please note: while participants are asked to not change their medication while admitted to the research unit. They can change medications during the follow-up phase.

We will ask subjects to speak with us by phone weekly for a month. They will also be asked to complete the TLFB (with study clinician) at this time (for the past week). Subjects will also be asked to complete the brief pain inventory, the Beck Depression Inventory (BDI); the Beck Anxiety Inventory (BAI); and will be asked about any change in medications (by phone).

Participants are followed by a study physician if they experience an adverse event (whether study related or not) until it resolves. This procedure will occur even if the follow up visits have been completed. Participants are also offered the option of being followed by a study physician until they have a visit with their health care provider.

Participants can opt to have the study PI communicate with their treating physician. This requires the completion of a release of information form. The communication between the PI and their physician would include a discussion of their diagnosis, previous treatment, study procedures, and outcomes.

After discharge from the study, participants are followed for 4 weeks with physician visits (telephone) and assessments (

I attest to follow the COVID-19 Safety Guidelines for Columbia Psychiatry and NYSPI Re-Entry outlined in the NYSPI Director's June 1st memo, which include but are not limited to:

- Infection Control/PPE – Guidelines
- Research participants will only come on-site if absolutely necessary for study procedures.
- No volunteers/externs on-site during Stage 1.
- Clinical research teams will screen their participants for COVID symptoms (night before and day of onsite visit, documenting this in the chart), and escort them in and out of the building.
- COVID/COVID-like symptoms in participants will be reported to the IRB via PRISM as an SAE.

Analysis and Outcomes

This protocol consists of an early feasibility study. Thus, all participants will receive active stimulation (no sham group) using an open-label design enrolling 12 participants. We have chosen this sample size in order to assess the following outcome measures: willingness to participate, tolerability, cognition, and pain. The willingness to participate will be assessed by measuring the percentage of participants who enroll out of those who are screened for the study. We expect that at least 20% will agree to enroll.

Criteria for Early Discontinuation

Define criteria that will be used to exit or drop subjects from the study and operationalize. Indicate the time points when such criteria will be applied, and describe the rating instruments, parameters, and thresholds that will lead to a decision

Protocol Summary Form

to terminate a subject's participation and the role of the person who will make these determinations. Studies which include a medication taper and discontinuation may be asked to include an independent medical monitor (an MD not on the study team) who will aid the study team in determining whether study discontinuation is needed. In addition, explain procedures for managing subjects who are withdrawn from the protocol.

For treatment studies: To minimize risks to subjects, operationalized drop-out criteria should be defined so that subjects who worsen, or in some cases, fail to improve, are removed from the study and offered standard care. The threshold for drop-out should consider the level of risk associated with non-improvement for the specific disorder, the availability of alternatives, and the typical required duration of treatment. For example, emergence of suicidal intent, or psychosis, should prompt immediate clinical evaluation and withdrawal from the study.

Participants will be discontinued if they have two seizures. In the event that they have one seizure the TEST dose will be lowered to 1/10th of the standard ECT dose (from 1/8th). The seizure will be discussed with the participant, including the plan to reduce the dose. If a participant decides to continue, this will be documented in their chart. If a participant has a seizure at 1/10th dose, they will be discontinued from the study.

Blood and other Biological Samples

Describe how the sample will be used and indicate, when relevant, the amount of the sample. The IRB wants to know that the sample is sufficient for the purposes of the study, but that sampling is limited to what is minimally necessary.

If you've indicated that you intend to store a sample for future use, indicate where the sample will be stored, how long the sample will be stored, and to what purposes the sample will eventually be put. Check the IRB website at <https://irb.nyspi.org/investigators/guidance/genetic-research> for specific guidance and additional information about future use of DNA samples.

Blood samples will be obtained for labs during screening (20ml) as will urine (<20 ml) for pregnancy testing. No samples will be stored for future use.

Assessment Instruments

List all assessment instruments, indicate who will administer them and their credentials/qualifications. Provide an estimate the duration of each measure. The IRB wants to know that assessments instruments are appropriate measures for the purposes of the study and are no more burdensome than necessary. The IRB will consider the burden of assessment instruments (in terms of time, sensitivity of material, etc.) in the risk/benefit analysis. Please attach copies or otherwise provide all non-standard instruments.

- a) The Hamilton Depression Rating Scale (HDRS) the 24-item assessment scale regarding symptoms of depression.
- b) Beck Depression Inventory (BDI): the 21 item self-report rating scale for depression
- c) Beck Anxiety Inventory (BAI): the 21 item self-report rating scale for depression
- d) The Young Mania Rating Scale: a widely used 11 item rating scales used to assess manic symptoms.

Protocol Summary Form

- e) The Columbia Suicide Severity Rating Scale (CSSRS): a suicide risk assessment that uses a series of simple, plain-language questions to assess thoughts of suicide.
- f) The Brief Pain Inventory (BPI): a short, self-administered questionnaire using a 0 to 10 scale, developed to quantify measures of pain.
- g) The Patient-Reported Outcomes Measurement Information System (PROMIS)-29, which assesses pain interference and quality of life.
- h) Columbia Autobiographical Memory Interview – short form (AMI-SF), which is used to assess memory changes in studies of ECT.
- i) Trail Making Test (TMT), Parts A and B, to assess executive function.
- j) The Stroop Color Word Test to also assess executive function.
- k) Repeatable Battery for the Assessment of Neuropsychological Status, which is a brief, individually administered battery to measure cognitive decline or improvement across five domains: immediate memory, visuospatial skills, language, attention, and delayed memory.
- l) Montreal Cognitive Assessment (MoCA), a quick (5-10 min) measure of cognition which uses a 10-item, 30-point (30=best score) scale.
- m) Clinical Global Impression (CGI) scale, a measure of symptom severity, treatment response and the efficacy of treatments as measured by a study physician.
- n) The Timeline Followback (TLFB): to obtain quantitative estimates of alcohol, tobacco, cannabis, and other drug use (including prescribed medications, like opioids and benzodiazepines). We will ask about substance use for time between screening and baseline.
- o) The Defense and Veterans Pain Rating Scale (DVPRS), a graphic tool that clinicians use to facilitate self-reported pain from patients, including the supplemental questions.

Sections to be completed for studies using IND/IDE Drugs and Devices.

Prior to the submission of any study involving a faculty held IND or IDE being approved by the IRB, the IND/IDE holder is required to submit a [form](#) signed by the IND/IDE holder and PI.

Which are applicable to your study: Drug Device Radiolabeled drug/compound

Off Label and Investigational Use of Drugs

Enter the information for all drugs to be used in this study:

Name of the drug	N/A
Manufacturer and other Information	
Approval Status (select one)	IND application is pending IND is approved

Protocol Summary Form

	No IND is required
IND #	
Who holds the IND (i.e., IND Sponsor). If other than PI/CU Investigator, type name of holder.	
Which applies:	FDA has determined the IND is not required FDA conditions are met (see "Rules") – Explain

Off Label and Investigational Use of Devices

Enter the information for all devices to be used in this study:

Name of the device	Thymatron
Manufacturer and other Information	Somatics, LLC
Approval Status (select one)	IDE is approved
IDE #	G210112
Who holds the IDE (i.e., IDE Sponsor). If other than PI/CU Investigator, type name of holder.	[name]
Is the device marketed?	No
Which applies:	FDA conditions are met, IDE approved

Off Label and Investigational Use of Radiolabeled Drugs / Compounds

Enter the information for all radiolabeled drug/compounds to be used in this study:

Name of the radiolabeled drug/compound	N/A
Manufacturer and other Information	

Protocol Summary Form

Approval Status (select one)	IND application is pending IND is approved RDRC approval is pending RDRC is approved No FDA/RDRC approval is required - Explain
IND #	
Who holds the IND (i.e., IND Sponsor). If other than PI/CU Investigator, type name of holder.	

Research Related Delay to Treatment

Research involving participants who are in need of treatment invariably involves delay to care, and this delay is associated with risk. Scheduling of procedures must be carefully organized to minimize delay. Other delay must involve only that minimally necessary to accomplish the aims of the research while respecting subject well-being and safety. Describe the delay, by virtue of research participation in this study, before a participant can receive treatment of known efficacy or standard care routinely offered in the community.

There is no delay to treatment.

Clinical Treatment Alternatives

Describe what other treatment or assessment options are available to subjects who do not participate in research.

The alternative is for subjects to not participate and to continue their usual care.

Risks/Discomforts/Inconveniences

"Risk" is a broad term used to convey the potential for harm, burden, and inconvenience related to research participation. Use this section to provide a comprehensive description of foreseeable physical, psychological, social, interpersonal, and economic risks introduced by the research. Include the source of the information. Consider both the probability and magnitude of harm and its impact. Describe the foreseeable harms associated with the research (untoward effects of a medication) and those related to delay to individualized treatment. Include data from the literature, and local data, if available, on risk rates and subject experiences with research procedures. Describe

Protocol Summary Form

procedures in place to minimize risk. In general, please create a numbered list of risks/categories of risk, and in general put the list in the order of significance or level of risk, the most significant risks should be listed first.

Risks of TEST: Previous experience with TEST is limited to patients with major depression, as described by Regenold et al, 2015. In this publication, TEST was delivered at 1/8th (which is the same as 1/16th age) the usual ECT dose for 7 seconds. Please note that a sister study is currently being performed at NIMH (in collaboration with our group here at NYSPI) by [name] using these same parameters. This protocol will use the same parameters as those used by Regenold et al (2015), as delineated in the procedures section.

Although not intended, a seizure is possible with the delivery of TEST. We do not expect a seizure to occur, as we are using the lower dose of TEST (reported in Regenold et al, 2015). If a seizure occurs, the subject will be monitored as though they have received ECT. Following this session, they will be informed of the seizure and asked if they would like to be removed from the protocol or continue. If they chose to continue, the dose will be lowered by 25%. If another seizure is elicited, they will be monitored appropriately and then removed from the protocol. Based on the previous publication by Regenold et al (2015) we do not expect a seizure to occur. Nonetheless, participants will be informed of this possibility and the need to stop the study.

The anesthesia medications include glycopyrrolate, methohexitol sodium, and succinylcholine. The risks of glycopyrrolate include anti-cholinergic effects (dilated pupils, increased body temperature, fast or irregular heart rate, blurred vision, constipation, drowsiness, dry eyes, dry mouth, flushing, and light sensitivity). The risks of methohexitol sodium include drowsiness, nausea, vomiting, stomach pain, chills or shivering, coughing, hiccups, muscle twitching, or mild skin rash or itching. The side effects of succinylcholine include jaw rigidity, hypotension, muscle fasciculation, respiratory depression, and salivary gland enlargement. Rare side effects include a severe allergic reaction, malignant hyperthermia, transient residual weakness due to prolonged succinylcholine activity (due to pseudocholinesterase deficiency, which is exceedingly rare [approximately 1 per 2000 to 5000 people] but would make succinylcholine last longer than 3-5 min), myoglobinuria/myoglobinemia, and arrhythmias.

Other risks of TEST include:

